10.2 Chronic GVHD Symptom Score

Patients will self-report symptoms and signs of cGVHD using the validated chronic GVHD Symptom Scale (Appendix E; section 17.5). Self-Reported symptom Scales will be obtained at baseline and weeks 8 and 16.

10.3 Steroid Use for Chronic GVHD

Patients will have their total daily dose of corticosteroids recorded at baseline, and at 8 and 16 weeks. In the case of alternate daily dosing of corticosteroids, the average daily dose will be recorded for study purposes.

10.4 Immune Assessment

Patients will undergo testing for immunologic function, performed at baseline, and at weeks 1, 2, 4, 6, 8, 9, 10, 12, 14 and 16. Testing will include: plasma banking and storage of additional mononuclear cells. Quantitative immune globulins will be tested at baseline and weeks 4, 8, 12, and 16.

CONFIDENTIAL

This document is confidential. Do not disclose or use except as authorized.

11. ADVERSE EVENT REPORTING REQUIREMENTS

11.1 Definitions

11.1.1 Adverse Event (AE)

An adverse event (AE) is any undesirable sign, symptom or medical condition or experience that develops or worsens in severity after starting the first dose of study treatment or any procedure specified in the protocol, even if the event is not considered to be related to the study.

Abnormal laboratory values or diagnostic test results constitute adverse events only if they induce clinical signs or symptoms or require treatment or further diagnostic tests.

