6. EXPECTED TOXICITIES AND DOSING DELAYS/DOSE MODIFICATIONS

Dose delays and modifications will be made using the following recommendations. Toxicity assessments will be done using the CTEP Version 4.0 of the NCI Common Terminology Criteria for Adverse Events (CTCAE) which is identified and located on the CTEP website at: http://ctep.cancer.gov/protocolDevelopment/electronic_applications/ctc.htm.

ECP is a standard-of-care therapy and its adverse events, for instance, hemorrhage from heparin exposure, cytopenias, and procedure intolerance (i.e. constitutional symptoms or cardiovascular instability) are rare.⁴⁵ Apheresis physicians will evaluate for procedure-related toxicities per the transfusion medicine SOP. ECP may also exacerbate underlying constitutional symptoms or cardiovascular instability, e.g. in the setting of mild dehydration, or suboptimally controlled hypertension. Such exacerbations are rare and transient and routinely managed by apheresis physicians per the transfusion medicine SOP.

If possible, symptoms should be managed symptomatically. In the case of toxicity, appropriate medical treatment should be used (including anti-emetics, anti-diarrheals, etc.).

All CTCAE grade 3 and higher adverse events experienced by participants will be collected, through the study and until the final week 16 study visit. Participants continuing to experience toxicity at the off study visit may be contacted for additional assessments until the toxicity has resolved or is deemed irreversible.

The dose modifications in section 6.2 are recommended but not mandatory for participants proceeding on indefinite extended-duration IL-2 at the end of the 16 week study.

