6.2 Dose Modifications/Delays

Toxicities are to be assessed according to the NCI Common Toxicity Criteria for Adverse Events (CTCAE), Version 4.0 (Appendix H; section 17.8)

- Anaphylaxis: Life threatening anaphylaxis related to IL-2 requires discontinuation of IL-2.
- Thrombotic microangiopathy: TMA during IL-2 therapy requires discontinuation of IL-2 if it is associated with CNS dysfunction, renal dysfunction requiring hemodialysis/CVVH, or need for hospitalization.
- CTC Grade 4 toxicity: Grade 4 non-hematologic toxicity related to IL-2 requires discontinuation of IL-2, unless it is an asymptomatic correctable lab test abnormality (e.g. uric acid).
- CTC Grade 3 toxicity: IL-2 will be withheld for Grade 3 non-hematologic toxicities related to IL-2, unless it is an asymptomatic and correctable lab test result abnormality (e.g. uric acid). If the toxicity resolves to grade 1 or below within 2 weeks, IL-2 can be restarted at 50% dose that will not be re-escalated. If the toxicity does not resolve in 2 weeks to grade 1 or below, or recurs to grade 3 or above after restarting IL-2, it will be discontinued. IL-2 may also be withheld for Grade 3 non-hematologic toxicities unrelated to IL-2 per physician discretion. If withheld, subsequent management is suggested per above guidelines.
- Expected non-hematologic toxicity: IL-2 can be withheld and/or restarted at 50% dose for less than grade 3 toxicity (local site reactions, persistent constitutional symptoms) depending on patient tolerability and the discretion of the treating physician.

CONFIDENTIAL

This document is confidential. Do not disclose or use except as authorized.

Phase II ECP and IL-2 for chronic GVHD

Version 2.0; August 15, 2016

- Severe hematologic toxicity: IL-2 will be withheld for severe declines in peripheral counts (ANC<500, Plts<10,000) not related to malignant disease relapse, infection or other etiologies. If counts improve (ANC>1000, Plts>20,000) within 2 weeks, IL-2 will be restarted at 50% dose and not re-escalated. If peripheral counts do not improve within 2 weeks, or drop again (ANC<500, Plts<10,000) after restarting IL-2, it will be discontinued.

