11.2 Procedures for AE and SAE Recording and Reporting

Reporting Participating investigators will assess the occurrence of AEs and SAEs at all participant evaluation time points during the study.

All CTC grade 3 or higher AEs and all SAEs whether reported by the participant, discovered during questioning, directly observed, or detected by physical examination, laboratory test or other means, will be recorded in the participant's medical record and on the appropriate study-specific case report forms.

The descriptions and grading scales found in the CTEP Version 4.0 of the NCI Common Terminology Criteria for Adverse Events (CTCAE) will be utilized for AE reporting. The CTEP Version 4.0 of the CTCAE is identified and located on the CTEP website at:

http://ctep.cancer.gov/protocolDevelopment/electronic_applications/ctc.htm.

All appropriate treatment areas should have access to a copy of the CTEP Version 4.0 of CTCAE.

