14.4 Analysis of Secondary Endpoints

Secondary endpoints include toxicity, immunologic effects, prednisone use, overall survival, progression-free survival, non-relapse mortality, and relapse. All analyses will be reported descriptively. Predictors for response will be explored in univariable analysis, including the impact of number of prior cGVHD therapies.

CONFIDENTIAL

This document is confidential. Do not disclose or use except as authorized.

14.5 Monitoring for Adverse Events.

Adverse events will be monitored closely. The monitoring guidelines will serve as a trigger for consultation with the DF/HCC Data Safety and Monitoring Committee (DSMC) for additional review, and are not regarded as formal stopping rules that would mandate automatic closure of study enrollment. ECP+IL-2 treatment was well tolerated in the 4 DFCI patients treated thus far.

If in the first 10 patients who start the IL-2 treatment, we observe 3 or more patients with grade 3 or higher treatment related toxicity, further accrual will be halted pending review by the DSMC. Depending on the findings of its review, the DSMC may recommend the permanent closure of enrollment or continuation of enrollment. With this design, the probability of halting the enrollment is 0.07 if the true but unknown grade 3 or higher treatment related toxicity rate is 10%, 0.62 if the rate is 30%, and 0.95 if the rate is 50%.

The same rule will be applied to non-relapse mortality, relapse, and cGVHD progression.

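### Section 11.1.1 can leave out laboratory toxicity managed only by holding, reducing or stopping IL-2, and Section 14.5 does not say whether its trigger counts it

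*Combined protocol and SAP*

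**What the plan says.** All references are to the combined protocol and SAP.

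- **Definition of an AE (Section 11.1.1).** "Abnormal laboratory values or diagnostic test results constitute adverse events only if they induce clinical signs or symptoms or require treatment or further diagnostic tests". A change to study drug is not among the qualifying consequences.
- **Dose rules (Section 6.2).** On counts alone, "IL-2 will be withheld for severe declines in peripheral counts (ANC<500, Plts<10,000) not related to malignant disease relapse, infection or other etiologies". The follow-on rule is "If peripheral counts do not improve within 2 weeks, or drop again (ANC<500, Plts<10,000) after restarting IL-2, it will be discontinued". For non-hematologic grade 4 toxicity related to IL-2, discontinuation applies "unless it is an asymptomatic correctable lab test abnormality (e.g. uric acid"), and the grade 3 rule has a parallel exemption. Section 5.4 likewise lists persistent or recurrent severe hematologic toxicity, and other grade 4 events that are not asymptomatic and correctable laboratory results, as reasons to end treatment.
- **Grading and collection (Section 6).** "Toxicity assessments will be done using the CTEP Version 4.0 of the NCI Common Terminology Criteria for Adverse Events (CTCAE"). Also, "All CTCAE grade 3 and higher adverse events experienced by participants will be collected".
- **Recording (Section 11.2).** Grade 3 or higher AEs and all SAEs go on the case report forms, including those "directly observed, or detected by physical examination, laboratory test or other means, will be recorded".
- **Safety trigger (Section 14.5).** "If in the first 10 patients who start the IL-2 treatment, we observe 3 or more patients with grade 3 or higher treatment related toxicity", accrual is halted pending DSMC review. The stated halting probabilities are 0.07, 0.62 and 0.95 at true rates of 10%, 30% and 50%.

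**The concern.** The dose rules and the AE definition apply different tests to a laboratory value. Sections 5.4 and 6.2 call a severe count decline a toxicity with no requirement for symptoms. Their exemptions for asymptomatic correctable results make sense only if an asymptomatic laboratory value can otherwise be a grade 3 or 4 toxicity. Section 11.1.1 asks instead for symptoms, treatment or further diagnostic tests. A patient could therefore have IL-2 held, reduced or ended for a toxicity that the AE section does not call an AE.

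Toxicity is a secondary objective (Section 1.3), and the only numerical safety rule counts patients with grade 3+ related toxicity. With 10 patients and a threshold of 3, one uncounted patient is enough to turn a halt into no halt. If sites resolve the wording differently, the toxicity rate and the trigger do not mean the same thing for every patient.

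**Working it through.** **Step 1: trace one case through the sections.** Take an asymptomatic ANC below 500 with no other cause apparent, found at a scheduled CBC. IL-2 is held, counts recover by the next scheduled CBC, and IL-2 is restarted under Section 6.2.

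| Section | Test | Result for this case |
|---|---|---|
| 6.2 | Count threshold | Severe hematologic toxicity; IL-2 withheld |
| 11.1.1 | Symptoms? | No |
| 11.1.1 | Treatment required? | Only if a drug hold is treatment; not defined |
| 11.1.1 | Further diagnostic tests required? | Not necessarily; see Step 2 |
| 11.2 | Grade 3+ AE or SAE? | Not recorded if 11.1.1 is not met |
| 11.4.1 | SAE report? | Expected grade 4 neutropenia and thrombocytopenia are listed as not requiring one |
| 12.2 | DSMC material | Names unexpected grade 2+ AEs; laboratory values on request |
| 14.5 | Grade 3+ related toxicity? | Not said whether this means 11.1.1 AEs or 6.2 toxicity |

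**Step 2: can the recheck be a routine draw?** Section 6.2 needs repeat counts within 2 weeks. The Study Calendar (Section 9) schedules CBC and chemistry at the end of weeks 8, 9, 10, 12, 14 and 16, with an extra draw of CBC, creatinine and LDH 4±2 days after IL-2 starts. The longest nominal gap is 12 − 10 = 2 weeks (likewise 14 − 12 and 16 − 14). A scheduled draw can therefore serve as the recheck, unless the ±4-day visit window stretches the gap.

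**Step 3: reproduce the plan's figures.** With X ~ Binomial(10, p),

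P(X ≥ 3) = 1 − [(1−p)^10 + 10p(1−p)^9 + 45p²(1−p)^8].

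- p = 0.10: 0.0702 (plan: 0.07)
- p = 0.30: 1 − [0.0282 + 0.1211 + 0.2335] = 0.6172 (plan: 0.62)
- p = 0.50: 1 − 56/1024 = 0.9453 (plan: 0.95)

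All three match.

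**Step 4: sensitivity to undercounting.** If a share f of patients with qualifying toxicity have only laboratory events and these go uncounted, the trigger sees p(1−f). The documents give no value for f, so every row after the first is an assumption. The true rate is 30% throughout.

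| f | Counted rate | P(halt) |
|---|---|---|
| 0 | 30% | 0.617 |
| 1/6 | 25% | 0.474 |
| 1/4 | 22.5% | 0.398 |
| 1/2 | 15% | 0.180 |

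For p = 0.25: 1 − [0.0563 + 0.1877 + 0.2816] = 0.474.

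**The case against.** A reader might infer that the sections flatly contradict each other and that laboratory toxicity will drop out of the 14.5 count. The documents do not support that.

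- Section 14.5 counts toxicity, not AEs. Toxicity is a separate assessment at each visit, and Sections 5.4 and 6.2 use that word for severe count declines. A plain reading could already include them.
- Sections 6 and 11.2 speak of adverse events, so they can be read as inheriting the 11.1.1 definition. In 11.2 the laboratory test is a means of detection; the section does not say that every grade 3+ value is an AE.
- The hematologic hold applies only when other causes are excluded. That will often need tests beyond a scheduled CBC, and the event then meets 11.1.1.
- Asymptomatic correctable non-hematologic values are exempt from the 6.2 hold and stop rules, so they are not cases of uncounted dose-limiting toxicity.
- Section 6.1.1 reports no neutrophil change and no platelet fall above 40% in the earlier experience. From the entry minimum of just over 50,000, a 40% fall leaves about 50,000 × 0.6 = 30,000, well above the 10,000 threshold. Evidence of hypothyroidism leads to work-up, so it meets 11.1.1.
- The trigger is expressly not a formal stopping rule.

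These points narrow the concern without removing it. No passage says that a hold is treatment, that a repeat count is a further diagnostic test, or which test 14.5 uses. The toxicity forms do not settle it: Section 11.4.2 has them carry non-serious adverse events, and the form schedule in 12.1.2 lists an adverse event form but no separate toxicity form. The treatment form or the recorded reason for removal (Section 5.6) may show the interruption, but not as a graded event.

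**Conclusion.** The gap is real but narrow. It covers laboratory toxicity that changes IL-2 treatment without symptoms, treatment or extra tests: mainly the count thresholds in Section 6.2, and any related grade 3–4 laboratory event that is asymptomatic but not correctable. On a literal reading, 11.1.1 and 11.2 leave such an event off the AE form, and 14.5 is silent on whether it counts.

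The size is unknown. The fall in halting probability from 0.62 to 0.47 assumes that one in six patients with qualifying toxicity has laboratory-only events and that all of these are missed; nothing in the documents supports that or any larger share. A fall to 0.32 (counted rate 20%) or 0.07 (10%) would need one third or two thirds to be missed. Only the direction is firm: omission lowers both the reported rate and the chance of review.

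Two limits apply. The 6.2 hematologic rule uses count thresholds rather than CTCAE grades. The documents also do not reproduce the CTCAE cut-offs (Appendix H points to a website), so no grade has been assigned to any particular value here.

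It does not follow that every grade 3+ laboratory value belongs in the trigger. That would bring in correctable results such as uric acid, which 6.2 sets aside, and possibly the early lymphocyte fall described in 6.1.1. If that moved the counted rate from 10% to 20%, the halting probability would rise from 0.07 to 0.32.

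**What to change.** Reconcile Sections 5.4, 6.2, 11.1.1, 11.2 and 14.5 on what is recorded and counted, leaving the dose rules as they are.

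1. **Section 11.1.1:** add a further qualifying consequence, namely that the laboratory abnormality leads to study treatment being withheld, reduced or stopped.
2. **Section 14.5:** state that grade 3 or higher laboratory toxicity meeting the amended definition counts toward the 3-of-10 trigger when at least possibly related to treatment.
3. **Section 14.4:** tabulate asymptomatic grade 3+ laboratory values that lead to no action separately, and do not count them in the trigger.

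The samples are already drawn, so no visit or test is added. The costs are slightly more AE form entries, a possibly higher reported toxicity rate, and a slightly higher chance of a DSMC review. The stated 0.07, 0.62 and 0.95 need no change, because they are functions of the counted rate; the amendment fixes what that rate includes.

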11.1.2 Serious adverse event (SAE)

A serious adverse event (SAE) is any adverse event, occurring at any dose and regardless of causality that:

- Results in death
- Is life-threatening. Life-threatening means that the person was at immediate risk of death from the reaction as it occurred, i.e., it does not include a reaction which hypothetically might have caused death had it occurred in a more severe form.
- Requires or prolongs inpatient hospitalization (i.e., the event required at least a 24-hour hospitalization or prolonged a hospitalization beyond the expected length of stay). Hospitalization admissions and/or surgical operations scheduled to occur during the study period, but planned prior to study entry are not considered SAEs if the illness or disease existed before the person was enrolled in the trial, provided that it did not deteriorate in an unexpected manner during the trial (e.g., surgery performed earlier than planned).
- Results in persistent or significant disability/incapacity. Disability is defined as a substantial disruption of a person's ability to conduct normal life functions.
- Is a congenital anomaly or birth defect; or
- Is an important medical event when, based upon appropriate medical judgment, it may jeopardize the participant and require medical or surgical intervention to prevent one of the outcomes listed above. Examples of such medical events include allergic bronchospasm requiring intensive treatment in an emergency room or at home; blood dyscrasias or

CONFIDENTIAL

This document is confidential. Do not disclose or use except as authorized.

convulsions that do not result in inpatient hospitalization, or the development of drug dependency or drug abuse.

Events **not** considered to be serious adverse events are hospitalizations for:

- routine treatment or monitoring of the studied indication, not associated with any deterioration in condition, or for elective procedures
- elective or pre-planned treatment for a pre-existing condition that did not worsen
- emergency outpatient treatment for an event not fulfilling the serious criteria outlined above and not resulting in inpatient admission
- respite care

11.1.3 Expectedness

Adverse events can be 'Expected' or 'Unexpected.'

11.1.3.1 Expected adverse event

Expected adverse events are those that have been previously identified as resulting from administration of the agent. For the purposes of this study, an adverse event is considered expected when it appears in the current adverse event list, the Investigator's Brochure, the package insert or is included in the informed consent document as a potential risk.

Refer to Section 6.1 for a listing of anticipated adverse events associated with IL-2.

11.1.3.2 Unexpected adverse event

For the purposes of this study, an adverse event is considered unexpected when it varies in nature, intensity or frequency from information provided in the current adverse event list, the Investigator's Brochure, the package insert or when it is not included in the informed consent document as a potential risk.

11.1.4 Attribution

Attribution is the relationship between an adverse event or serious adverse event and the study treatment. Attribution will be assigned as follows:

- Definite – The AE is clearly related to the study treatment.

CONFIDENTIAL

This document is confidential. Do not disclose or use except as authorized.

- Probable – The AE is likely related to the study treatment.
- Possible – The AE may be related to the study treatment.
- Unlikely - The AE is doubtfully related to the study treatment.
- Unrelated - The AE is clearly NOT related to the study treatment.

11.2 Procedures for AE and SAE Recording and Reporting

Reporting Participating investigators will assess the occurrence of AEs and SAEs at all participant evaluation time points during the study.

All CTC grade 3 or higher AEs and all SAEs whether reported by the participant, discovered during questioning, directly observed, or detected by physical examination, laboratory test or other means, will be recorded in the participant's medical record and on the appropriate study-specific case report forms.

The descriptions and grading scales found in the CTEP Version 4.0 of the NCI Common Terminology Criteria for Adverse Events (CTCAE) will be utilized for AE reporting. The CTEP Version 4.0 of the CTCAE is identified and located on the CTEP website at:

http://ctep.cancer.gov/protocolDevelopment/electronic_applications/ctc.htm.

All appropriate treatment areas should have access to a copy of the CTEP Version 4.0 of CTCAE.

11.3 Reporting Requirements

For multi-site trials where a DF/HCC investigator is serving as the principal investigator, each participating investigator is required to abide by the reporting requirements set by the DF/HCC. The study must be conducted in compliance with FDA regulations, local safety reporting requirements, and reporting requirements of the principal investigator.

Each investigative site will be responsible to report SAEs that occur at that institution to their respective IRB. It is the responsibility of each participating investigator to report serious adverse events to the study sponsor and/or others as described below.

11.4 Reporting to the Study Sponsor

11.4.1 Serious Adverse Event Reporting

CONFIDENTIAL

This document is confidential. Do not disclose or use except as authorized.

Phase II ECP and IL-2 for chronic GVHD

[figure not shown]
Version 2.0; August 15, 2016

DF/HCC: All serious adverse events that occur after the initial dose of IL-2 study treatment, during treatment, or within 30 days of the last dose of treatment must be reported to the DF/HCC Overall Principal Investigator on the local institutional SAE form. This includes events meeting the criteria outlined in Section 11.1.2, as well as the following:

- Grade 2 (moderate) and Grade 3 (severe) events that are unexpected and at least possibly related/associated with the intervention.
- All Grade 4 (life-threatening or disabling) events that are unexpected and not specifically listed in the protocol as not requiring reporting. Grade 4 expected events related to stem cell transplantation that do not require reporting as SAEs include: neutropenia, neutropenic fever, thrombocytopenia, minor bleeding episodes (e.g. epistaxis), rashes, diarrhea, infections (e.g. pneumonia, line sepsis, cellulitis), VOD, TMA and GVHD as these are expected events related to stem cell transplantation.
- All Grade 5 (fatal) events while the participant is enrolled and actively participating in the trial OR when the event occurs within 30 days of the last study intervention.

Note: If the participant is in long term follow up, report the death at the time of continuing review.

Participating investigators must report each serious adverse event to the DF/HCC Overall Principal Investigator within 24 hours of learning of the occurrence. In the event that the participating investigator does not become aware of the serious adverse event immediately (e.g., participant sought treatment elsewhere), the participating investigator is to report the event within 24 business hours after learning of it and document the time of his or her first awareness of the adverse event. Report serious adverse events by telephone, email or facsimile to:

Within the following 24-48 hours, the participating investigator must provide follow-up information on the serious adverse event. Follow-up information should describe whether the event has resolved or continues, if and how the event was

CONFIDENTIAL

This document is confidential. Do not disclose or use except as authorized.

Phase II ECP and IL-2 for chronic GVHD

Version 2.0; August 15, 2016

treated, and whether the participant will continue or discontinue study participation.

[figure not shown]
